1.4 Protocol establishment

PD Dr. med. [name], [name], [name]

2 Summary

Functional imaging diagnostics is becoming increasingly important due to the steadily growing knowledge of physiological processes in many diseases. Likewise, in peripheral arterial occlusive disease (PAD), new insights into the pathomechanism of the disease are continuously being gained [1]. Similarly, this increases the need for new non-invasive imaging methods that are able to visualize the functional level of the disease progression and thus enables the diagnosis at an early stage.

Recent studies indicate that it may be feasible to use multispectral optoacoustic tomography (MSOT) to visualize hemodynamics and the fibrotic muscle remodeling process in PAD [2]. For a better understanding of the distribution pattern, the exploration of a 3D technique is a next necessary step in imaging. This may show a possible existing heterogeneity of these molecules.

The aim of this exploratory pilot project is to image muscle perfusion of the lower extremity in three dimensions using the MSOT method and to verify its feasibility. The advantage of 3D imaging is, beyond the anatomical topography of the muscle, to map a three-dimensional representation of the perfusion situation based on muscle oxygenation.

For this purpose, six patients of different symptomatic PAD stages and a healthy control of two volunteers will be included and examined by the means of longitudinal MSOT scans in the area of the gastrocnemius muscle. To evaluate the current stage of the disease or to exclude relevant PAD in the healthy control population, non-invasive examination measures commonly used in routine diagnostics of PAD will be applied. In addition to the relevant risk factors, coexisting comorbidities and the current medication, these include the recording of the ankle-brachial index (ABI), color-coded duplex sonographic vascular imaging (CCDS) and a treadmill examination.

3 Responsibilities

3.4 Funding source

Vascular Surgery Department; internal funding pending application for external funding.

4 Scientific Background

Starting in 2021, a CE-certified Multispectral Optoacoustic Tomograph (MSOT) will be available at the University Hospital Erlangen (Children's and Adolescent's Hospital). It will allow transcutaneous in-vivo measurements of soft tissue. Comparable to sonography, this allows noninvasive, quantitative imaging of the constitution and oxygenation of target tissues such as muscles.

In MSOT, similar to conventional sonography, a transducer is placed on the skin and instead of sound, energy is delivered to the tissue through flashlights. This leads to a constant alternation of minimal expansions and contractions (thermoelastic expansion) of individual tissue components or molecules. The resulting sound waves can be detected by the same examination probe. Previous studies have shown that quantitative determination of hemoglobin can provide information on blood flow and inflammatory activity in the intestine of patients with Crohn's disease [3, 4]. In the CE-certified MSOT device (Acuity Echo, iThera Medical GmbH, Munich), a spectrum of laser light can be used, which enables the detection of hemoglobin and its oxygenation levels as well as the detection of other markers like collagen and lipid, which has already been successfully measured, validated and reproduced in 2D imaging in pre-studies. Figures 1 and 2 show examples of the feasibility of this imaging method with selected MSOT parameters as examples.

Holzwarth et al. were already able to gain knowledge about the 3D reconstruction from 2D photoacoustic image slices using an optical pattern and the method's feasibility using phantoms as well as in-vivo measurements of the forearm in healthy volunteers [5]. This leads to the evaluation of the method as a diagnostic application for muscular perfusion imaging in patients with vascular dysfunction.

Until now, there are few noninvasive measurement methods besides MSOT that can provide transcutaneous information about 3D muscle perfusion. Even topographic muscle imaging from computed tomographic (CT) or magnetic resonance imaging (MRI) reconstructions carries certain risks despite its routine in daily clinical use. For example, CT examinations require radiation exposure, and MRI examinations exclude patients with certain comorbidities or previous performed surgeries (loose metal parts such as pacemakers) and patients with restlessness.

In this explorative pilot study, a 3D reconstruction of the calf muscle using MSOT techniques to visualize muscle perfusion will be investigated for the first time in a PAD patient group. Patients with different PAD stages and a control collective of healthy volunteers as a comparison group will be included. Different optical patterns offer diverse possibilities for the calculations of the 3D reconstruction. Therefore, this study will also evaluate the feasibility of the two options and analyze the measurements to optimize the 3D procedure.

[figure not shown]

Figure 1: Visualization showing optoacoustic signal of perfusion parameters in 2D scans, from left to right: B-scan ultrasound (b/w RUCT), signal at 800 nm wavelength, Hb signal (blue), HbO₂ signal (red) of the medial muscle head of the gastrocnemius muscle (transversal plane). Unpublished original data.

[figure not shown]

Figure 2: Visualization showing optoacoustic signal of connective tissue structures in 2D scans, from left to right: B-scan ultrasound (b/w RUCT), signal at 800 nm wavelength, collagen signal (turquoise), lipid signal (yellow) of medial muscle head of gastrocnemius muscle (transversal plane). Unpublished original data.

References

1. Signorelli, S.S., et al., *Pathophysiology of chronic peripheral ischemia: new perspectives*. Therapeutic Advances in Chronic Disease, 2020. **11**: p. 1-15.
2. Karlas, A., et al., *Multispectral optoacoustic tomography of muscle perfusion and oxygenation under arterial and venous occlusion: A human pilot study*. Journal of Biophotonics, 2020. **13**(6): p. e201960169.
3. Knieling, F., et al., *Multispectral Optoacoustic Tomography for Assessment of Crohn's Disease Activity*. The New England Journal of Medicine, 2017. **376**(13): p. 1292-1294.
4. Waldner, M.J., et al., *Multispectral Optoacoustic Tomography in Crohn's Disease: Noninvasive Imaging of Disease Activity*. Gastroenterology, 2016. **151**(2): p. 238-40.
5. Holzwarth, N., et al., *Tattoo tomography: Freehand 3 D photoacoustic image reconstruction with an optical pattern*. International Journal of Computer Assisted Radiology and Surgery, 2021. **16**: p. 1101-1110.

5 Study Objectives

The aim of this pilot study is to implement a three-dimensional reconstruction of the perfusion situation based on two-dimensional longitudinally measured MSOT scans to visualize the topographical distribution of oxygenated hemoglobin in the calf muscle using MSOT.

5.1 Primary/secondary objectives and hypotheses

Primary hypothesis:

- MSOT provides topographic perfusion imaging of the gastrocnemius muscle using 3D reconstruction.

Secondary hypotheses:

- Collected 3D MSOT parameters in muscles of patients with PAD differ visually depending on the clinical severity of PAD, classified according to Fontaine and Rutherford.
- Collected 3D MSOT parameters in muscles of patients with PAD differ quantitatively depending on the clinical severity of PAD, classified according to Fontaine and Rutherford.
- Collected 3D MSOT parameters in muscles of patients with PAD show improved diagnostic accuracy than 2D MSOT measurements.

Primary objective:

- Visualization of a perfusion topogram based on oxygenated hemoglobin in the calf muscle of patients with PAD using 3D MSOT.

Secondary objectives:

- Acquisition of different MSOT values at multiple wavelengths in the range from 660 nm up to 1100 nm in static and longitudinal measurements.
- Acquisition of the quantitative hemoglobin signal (oxygenated/deoxygenated) as unmixed spectrum.
- Acquisition of the quantitative lipid signal as unmixed spectrum
- Acquisition of the quantitative collagen signal as unmixed spectrum
- If an MRA is already available regardless of study participation, validation of the accuracy of the MSOT 3D reconstruction using an overlay.

5.2 Study type

Exploratory pilot study

6 Outcome Measures

All measurements with MSOT are performed before and after gait exposure in the area of the medial part of the gastrocnemius muscle. Different MSOT wavelengths in the range from 660 nm to 1100 nm are assessed. Various parameters calculated from the measured wavelengths are also taken into account for the evaluation (Hb, HbO₂, Hbtot, collagen, lipid, sO₂).

6.1 Primary outcome measures:

- MSOT topogram showing perfusion (oxygenated/deoxygenated/total hemoglobin) of the gastrocnemius muscle
 - *These outcome measures are collected non-invasively using MSOT.*

6.2 Secondary outcome measures:

- Topographic imaging of lipid signal and collagen signal using MSOT
 - *These outcome measures are collected non-invasively using MSOT.*
- 3D reconstruction of the longitudinal measurements using two different pattern designs
 - *These outcome measures are collected non-invasively using MSOT.*
- Acquisition of static 2D MSOT measurements before and after gait exposure
 - *These outcome measures are collected non-invasively using MSOT.*
- Acquisition of the flow profile of the common femoral artery and popliteal artery using CCDS
- Acquisition of the Ankle-brachial-index
- Acquisition of the current walking distance standardized by treadmill examination
- Acquisition of the current walking distance standardized by treadmill examination (Excluding patients with PAD in chronic critical stage III or IV according to Fontaine)
- Acquisition of the PAD stage according to Fontaine and Rutherford
- Recording of relevant secondary diseases from the patient's file
- Recording of relevant previous operations from the patient's file
- Recording of current medication from the patient's file

7 Study Design

7.1 Monocentric/multicentric

This is a monocentric exploratory pilot study with prospective data collection.

7.2 Study arms: intervention/control

Interventions are not planned. The study will be conducted in two stages. First, the presentability of 3D reconstruction of the calf muscle will be tested in two healthy volunteers. Subsequently, a representative patient collective of different PAD stages will be examined with the method.

7.3 Randomization

Randomization is not planned.

7.4 Blinding

The investigator will be blinded during the measurement and data analysis. The blinding of the investigator is done by the investigator only performing the MSOT measurements and not knowing the results from the previous examinations (ABI, CCDS, treadmill, PAD stage).

Blinding of the patients/healthy study participants is not necessary.

[figure not shown]

Figure 3 Graphical presentation of the study flow with the planned measurements.

8 Study Population

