8.1 Eligibility criteria

Inclusion criteria:

- Patients with manifest PAD stages II-IV according to Fontaine or healthy volunteers
- Adults (>18 years) who are able to give their consent

Definition of patient group:

- Patients with PAD IIa/IIb/III/IV according to Fontaine who come in for a routine presentation of the vascular surgery consultation hours.

Definition of healthy volunteer group:

- no PAD previously known
- no diabetes mellitus previously known
- no chronic renal insufficiency previously known
- no symptoms in the sense of a Claudicatio intermittens
- ABI with normal value

Exclusion criteria:

- Patients with PAD stage I according to Fontaine
- Healthy volunteers with pre-existing diabetes mellitus, chronic renal failure, or abnormal ABI
- Underage persons
- Missing consent form
- Exclusion due to safety concerns of the study physician (patient with a physical, mental or psychiatric illness which, in the opinion of the study physician, would compromise the safety of the patient or the quality of the data and thus make the patient an unsuitable candidate for the study)

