9.2 Measures

After informing the patients, all study participants will be asked to provide information about their existing illnesses, previous operations, and current medication. If available, the electronic patient file will be used for this purpose, otherwise these data will be collected by means of a medical history interview. Of particular interest are diseases, operations and medication related to the vascular system. This is followed by measurement of the ABI. This parameter is used in vascular medicine to estimate the

severity of PAD. For healthy study participants, the measurement of the ABI is to be regarded as a screening examination. Study participation of healthy volunteers requires an unremarkable value in the ABI measurement (the handling of incidental findings during screening is presented in chapter 13). Prior to this measurement, a rest period in lying position of at least 10 minutes should be observed. Measurements of occlusion pressures on both legs and arms are then performed. The examination of the ABI takes a maximum of 20 minutes, including the preceding rest period, and would also be recorded in PAD patients independently of study participation during the inpatient stay as part of routine diagnostics. Afterwards, a CCDS of the femoral arteries is performed at rest. The CCDS is used to determine the flow profile of the examined vessels and allows an estimation of constrictions or occlusions in these. For this purpose, the patient/proband remains lying on the examination couch. Depending on the examination conditions (individual anatomy of the vessels, body size, etc.), this examination takes about 10 minutes. This examination takes place as part of routine vascular surgery diagnostics.

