The actual current walking distance is used to classify and categorize the severity of PAD and should be recorded by a treadmill examination. Under medical supervision, the patients/probands are to complete the greatest possible distance on the treadmill at a 12% incline and 3 km/h (standard setting). If the 12% incline is not practicable for the patient, the incline will initially be reduced to 6%. If this is also not practicable, it will be reduced to 0% incline. The walking distance is recorded in meters. Since the first 200 meters in particular are important for the classification of PAD, the examination will be terminated by the study physician when a walking distance of more than 500 meters has been reached. The treadmill examination takes about 15 minutes and is usually performed for patients in stage II as part of routine vascular surgery diagnostics. For patients in stage III or IV, the examination is not part of the routine diagnostics and only takes place within the framework of study participation if the study physician declares this medically justifiable.

All examinations mentioned so far take place in the facilities of the Department of Vascular Surgery.

For the MSOT measurements, the CE-certified MSOT device of the Pediatric and Adolescent Clinic of the University Hospital Erlangen is used. Since the MSOT device is located in the facilities of the Children's Hospital, the patients/probands are transported there in a wheelchair after the examinations mentioned so far. It is

important that there is no physical exertion during the transport, as this could falsify the MSOT values. The transport takes about 15 minutes. Subsequently, MSOT measurements are taken with the MSOT device over a length of about 6 cm in the longitudinal section of the medial head of the gastrocnemius muscle (in patients in the area of the affected leg). Multiple measurements of both legs are performed with different foils applied in a standardized manner.

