If necessary, the area of the lower leg to be examined will be shaved to avoid artifacts from dark colored hairs. The ultrasound gel is applied to the calf. Then a foil imprinted with an "N" is applied and fixed. The proband ID is noted on the foil. Above the imprint, an initial static measurement is taken at rest and subsequently a longitudinal measurement is taken, which can be reconstructed in 3D. At least three longitudinal 2D measurements are made or repeated until a promising result is obtained. The same procedure is repeated with a foil imprinted with a trident.

The examination is performed analog to sonography above the corresponding skin layers without further invasive procedures. The anatomical region can be localized by means of built-in B-scan sonography; subsequently, the corresponding optoacoustic signals can be derived. The duration per anatomical region is limited to 5 minutes; the study participants can remain in a relaxed position during the examination; assistance, e.g., breathing maneuvers, is not necessary.

Subsequently, the patient will complete a defined walking distance of 150 meters under medical supervision. The foils printed with tridents remain fixed to the calf muscles for this purpose. Afterwards, the medial head of the gastrocnemius muscle is measured again using MSOT. Therefore, the affected leg of patients is first examined in a static 2D-measurement, then in longitudinal measurements and again in a static 2D-measurement. In healthy probands, the right leg is measured first.

After a second defined walking distance of 150 meters, the unaffected leg is examined in patients and the left leg in healthy probands in the order described above.

In the context of so far unpublished preliminary studies, it was indicated that an active muscle exercise between the two examinations by MSOT causes a change of the perfusion parameters and can possibly unmask a stenosis in the supply area of the lower legs. If the patient is unable to walk 150 meters between the two MSOT measurements due to pre-existing conditions or due to the severity of the PAD stage,

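### Section 7.4 claims more blinding than the scan procedure allows, and section 9.2 lets the result decide when to stop scanning, with no rule for which run is analysed

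*Combined protocol and SAP*

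**What the plan says.** **Blinding.** Section 7.4 opens with "The investigator will be blinded during the measurement and data analysis". The next sentence gives the means: "the investigator only performing the MSOT measurements and not knowing the results from the previous examinations (ABI, CCDS, treadmill, PAD stage".

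**Group.** Section 7.2 runs the study in two steps: "First, the presentability of 3D reconstruction of the calf muscle will be tested in two healthy volunteers", with the patients afterwards. Section 8.1 defines a volunteer partly by "ABI with normal value" and by no known PAD. Section 9.2 repeats the ABI condition: "Study participation of healthy volunteers requires an unremarkable value in the ABI measurement".

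**Leg.** Section 9.2 places the scan over the "medial head of the gastrocnemius muscle (in patients in the area of the affected leg" and adds "Multiple measurements of both legs are performed with different foils applied in a standardized manner". After exercise, patients have the affected leg scanned first and volunteers the right leg. The other leg follows after a second walk.

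**Runs.** For the resting scans, section 9.2 says "At least three longitudinal 2D measurements are made or repeated until a promising result is obtained", and the same is done with the second foil. Time per anatomical region is capped at 5 minutes (also in section 10.3). For the post-exercise longitudinal scans the section gives neither a number of runs nor a repeat rule.

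**Use of the data.** Section 5.1 has secondary hypotheses that 3D parameters differ visually and quantitatively with clinical severity among patients. Section 11 plans a mainly descriptive evaluation and a paired t-test before versus after exercise. Section 12.2 pseudonymizes the data before analysis.

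**The concern.** There are two separate weaknesses.

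The first is the scope of the blinding claim. The opening sentence of 7.4 is general, while the mechanism covers four results and the scan procedure depends on group and leg. A report that repeats the opening sentence would tell readers that more was hidden than was.

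The second is the repeat rule. If an operator scans until a run looks promising, and nobody has fixed which run is reconstructed and analysed, the result itself can decide which data are used. The severity comparisons are where this matters. They include a visual judgement, which is the kind of reading most open to expectation, and they rest on two patients per stage.

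**Working it through.** **1. What 7.4 hides, against what the procedure discloses**

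| Item | Listed as hidden in 7.4? | Disclosed by following the protocol? |
|---|---|---|
| Patient or volunteer | No | Yes: volunteers come first (7.2), and leg order after exercise differs by group (9.2) |
| Affected leg | No | Yes: it sets scan site and order (9.2) |
| ABI, volunteers | Yes | Yes: a normal value is required for entry (8.1, 9.2) |
| PAD status, volunteers | Yes, as stage | Yes: no known PAD is part of the definition (8.1) |
| ABI, CCDS, treadmill, stage in patients | Yes | Not directly |

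The general claim fails for group and affected leg. The narrower claim fails for the volunteers' ABI and PAD status. For stage II versus III versus IV, nothing directly contradicts it.

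**2. The exercise cue.** Section 9.2 lets the walk be shortened in steps from 150 m to 100, 50 and 25 m, then replaced by standing or seated exercise, partly because of PAD severity. This is an imperfect sign of stage. It arises after the resting scans, so it cannot affect how they are acquired. It could affect post-exercise scanning, or later choice and reading of runs, but only if the operator or reader learns of it. The available text does not say whether they do.

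**3. How many runs are open to choice.** Assume both foils are used on both legs and three runs are the minimum.
- Per participant at rest: 3 runs × 2 foils × 2 legs = 12.
- Six patients: 12 × 6 = 72.
- If one run per foil and leg is analysed (an assumption): 2 × 2 × 6 = 24 picks, leaving 72 − 24 = 48 runs unused.
- If all acceptable runs are averaged, there is no pick. The documents do not say which applies.

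**4. What a result-driven pick can do: illustration only.** Let runs on the same leg and foil be independent and normal, with run-to-run SD as the unit. Independence and normality are assumptions, and the documents give no SD. The expected highest of three is 3 / (2√π) = 3 / 3.545 = 0.846, so the shift is about 0.85 SD. Simulation with 400,000 draws also gave 0.846. It gave about 1.16 for the highest of five and 1.54 for the highest of ten. The 5-minute cap limits how many runs are possible, but no number is stated.

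**5. What a fixed rule does.** Under the same assumptions, a rule set in advance that does not look at signal height has an expected shift of 0. For stage II (n = 2) against III and IV together (n = 4), the standard error from run noise alone is √(1/2 + 1/4) = 0.87 SD with one run per patient. With the mean of three runs it is 0.866 / √3 = 0.50 SD.

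**The case against.** The strongest reply is that 7.4 defines its own terms. Its second sentence limits blinding to four results, and affected leg is not among them. Knowing who is a volunteer, or which leg is affected, does not by itself bias hypotheses about severity among patients, because volunteers are outside those hypotheses. *Promising* follows a sentence about scans that can be reconstructed in 3D, so it may mean no more than technically usable. The 5-minute cap limits repetition. Section 12.2 requires pseudonymization before analysis, and under section 12.1 the study director keeps the identification list. The study is a mainly descriptive feasibility pilot.

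Most of this stands, and it sets the size of the point. Three things remain. The opening sentence of 7.4 is still wider than its mechanism, and for volunteers even the listed ABI and PAD status are known. The text does not say that *promising* means reconstructable; if it does, writing that down costs nothing. Pseudonymization replaces names, but the plan does not say that codes hide group, leg, stage or exercise type, so its protection is partial.

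A reader might infer two stronger things:

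- *That blinding to stage is broken among patients.* The documents do not show this. The exercise cue is conditional, the walk is under medical supervision that need not be the operator's, and 7.4 confines the investigator to scanning. Figure 3 and parts of section 3 were not available here and may name who scans and who reads, so no missing role is claimed.
- *That a severity gradient could be manufactured*, for example a gap of 2 × 0.846 = 1.69 run SDs from always taking the highest of three runs in patients thought mild and the lowest in those thought severe. That needs a cue that is always right, selection in every patient and one analysed run per foil and leg. None of these is in the documents, and with no cue the gap is 0.

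**Conclusion.** The point holds in a limited form and is minor. The statement in 7.4 overclaims: acquisition is not blinded to group or affected leg and, for volunteers, not to a normal ABI or the absence of known PAD. Stage among patients may well be masked as stated. Separately, the repeat rule for resting scans, with no stated rule for which run is used, allows run choice to follow the result in the visual and quantitative severity comparisons.

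No size of bias can be derived from the documents. The 0.85 SD shift rests on independent normal runs and on always taking the highest of three; it shows a mechanism and does not estimate what will happen. The primary topogram asks whether the image can be made, and the paired t-test compares participants with themselves, so knowledge of group or stage has little bearing on either. The main harm is a report that claims more blinding than there was.

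**What to change.** 1. **Section 7.4.** Limit the statement to what is hidden, for example: *For patients, the operator does not know ABI, CCDS, treadmill result or PAD stage. Acquisition is not blinded to group or affected leg.* Reconcile this with sections 7.2 and 9.2, and say whether the operator or reader learns how the exercise was adapted.
2. **Section 9.2.** Replace the undefined stopping condition with a technical criterion set in advance that does not depend on signal height, for example pattern readable and muscle in view over the planned 6 cm. Fix in advance that either all acceptable runs are averaged or the first acceptable run is used. Averaging keeps the replicates; the first-run rule is simpler. Log the number of runs taken.
3. **Reading.** Build on the pseudonymization in section 12.2: rate the patients' reconstructions under codes that do not show stage or exercise type, and record the visual rating before stage is revealed.

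Reconstruction settings can stay open, since section 4 makes optimizing the 3D procedure part of the study.

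**Cost.** A short text change in 7.4 and 9.2 and coding of six patients' files; no extra participants or scans. The blinding claim becomes weaker, patient images are read slightly later, and an operator who is also the reader may recall some scans.
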